4.3.2.2 Insomnia Severity Index (ISI)

The ISI is a 7-item instrument that quantifies the participants perception of insomnia severity in the last 2 weeks (Bastien et al, 2001) and is collected during screening, at week 4 and at week 12/EoT. The items refer to: severity of sleep onset, sleep maintenance and early morning wakening problems, satisfaction with sleep pattern, noticeability of sleep problems by others, distress caused by the sleep difficulties and interference of sleep difficulties with daytime functioning. It is scored on a 5-point Likert scale from 0 to 4. The scores for each

Version 2.0 Page: 28 of 57

item are summed to produce the total score (maximum of 28) which allow categorization of severity of insomnia.

Total score severity categories:

- 0-7 = No clinically significant insomnia
- 8–14 = Subthreshold insomnia
- 15–21 = Clinical insomnia (moderate severity)
- 22–28 = Clinical insomnia (severe)

The baseline value will be the earliest assessment on day 1 or day 2. If both day 1 and day 2 assessment is not available, the baseline value will be the latest available assessment on or before day 4. Only assessments where ≥ 8 days of the 14-day recall period are outside of the impact duration of prohibited hormonal therapies and medication potentially confounding efficacy will be included. Details regarding the prohibited medications together with the impact duration are described in Section 6.3.

The absolute values and change from baseline values for ISI total score will be summarized using descriptive statistics by study treatment and week. The change from baseline over time by study treatment will be shown using line plots for means and 95% CI.

The ISI severity categories will be summarized using frequency tables by study treatment and week. Stacked bar charts showing the composition of severity categories at each week by treatment group will be produced.

In addition, the number and percentage of each response for each individual item will be summarized using frequency tables by study treatment and week. Stacked bar charts will also be produced showing the composition of responses for each item by treatment group and week.

4.4 Exploratory/Other Endpoints Analysis

For all exploratory endpoints, the ICEs will be handled according to the treatment policy. No missing data imputation is planned for these endpoints. Analyses will be performed using the FAS.

4.4.1 Other PSG Exploratory Endpoints

- Change from baseline at week 4 and week 12 in PSG measures of sleep onset, duration, and continuity: LPS, TST, SOL, SOLN1, WTDS, EMWT, TWT, percentage of TWT, NAW, mean duration of awakenings, WASO by each quarter of the night.
- Change from baseline at week 4 and week 12 in measures of different sleep stage duration: time and percent in stage N1 sleep, time and percent in stage N2 sleep, time and percent in stage N3 sleep, time and percent in non-REM sleep, time and percent in REM sleep, REM onset latency from sleep onset.
- Change from baseline at week 4 and week 12 in other PSG measures: arousal index and number of stage shifts.

The calculation of the change from baseline to week 4 and 12 will be analogous to the primary endpoint (Section 4.2.1). See Section 6.2.1 for more details on the definition for each parameter as measured by PSG.

Version 2.0 Page: 29 of 57

The actual values and change from baseline will be summarized using descriptive statistics by study treatment and week. The change from baseline over time by study treatment will be shown using line plots for means and 95% CI. In addition, descriptive statistics for actual and change from baseline will be summarized by study treatment and individual nights (i.e., baseline night 1, baseline night 2, week 4 night 1, week 4 night 2, week 12 night 1, week 12 night 2).

4.4.2 Sleep Diary (SD) Related Endpoints

• Change from baseline in subject-reported measures (as determined by SD) of sleep onset, duration, and continuity over time: sWASO, sLPS, sTST, sTIB, sSE, sNAW

Participant's assessment of sleep disturbance will be recorded electronically daily using the Sponsor developed SD. The SD is completed in the morning after waking up (calendar day) to assess the participant's sleep disturbance during the previous night (diary day). The SD consists of 6 items that assess the total sleep time duration by asking for time of going to bed, falling asleep and waking up, as well as duration spent in bed, number and duration of awakenings during the night.

SD assessments that do not logically make sense will be excluded from the analysis but will still be included in the listings. Assessments that satisfy one or more of the below criteria will be excluded:

- 1. If time taken to fall as $leep \ge duration$ between time going to bed and time waking up
- 2. If total duration of awakenings ≥ duration between time going to bed and time waking up
- 3. If total duration of awakenings \geq duration between time going to bed and time waking up time taken to fall asleep
- 4. If time going to bed is between 06:00 and 16:00 (inclusive), and duration between time going to bed and time waking up is <1 hour or ≥ 16 hours.
- 5. If time waking up is between 12:00 23:59 (inclusive), and duration between time going to bed and time waking up is <1 hour or \geq 16 hours.
- 6. If time going to bed = time waking up
- 7. If time going to bed = time getting out of bed

Subject-reported parameters to be analyzed will be calculated using items from the SD as detailed in Table 4-6:

Table 4-6: Definition of Subject-Reported Parameters from SD

Subject-reported parameter	SD item(s)
sWASO (mins)	Item 4: total duration of awakenings
sLPS (mins)	Item 2: time taken to fall asleep
sTST (hours)	Time between going to bed (Item 1) and waking up in the morning (Item 5) minus the time taken to fall asleep (Item 2) and total duration of awakenings (Item 4)
sTIB (hours)	Time between going to bed (Item 1) and getting out of bed (Item 6*)

Version 2.0 Page: 30 of 57

sSE (%)	(sTST / sTIB) * 100
sNAW	Item 3: total number of times woke up in the night

^{*} If time getting out of bed (item 6) is before time waking up in the morning (item 5), then time getting out of bed will be set as the same time as waking up.

For the analysis, weekly mean values will be used. The mean daily value for each study week will be calculated by using available data during that week as:

For a particular parameter:

total value of the parameter during that week

total number of available days with morning data for that parameter during that week

Study week will be assigned using the definition in Section 4.1.2 using diary day as the date of observation. Data entered on the morning after the start date of treatment / randomization date will not be used in the calculation of baseline value but will be considered post-baseline.

The mean daily value can be derived if a value is provided for at least 4 out of 7 days with morning data, otherwise the value will be set as missing. The baseline value will be calculated similarly using all available days with morning data during the 14 days prior to starting treatment. A minimum of 7 days should be available for the derivation of the baseline value. Only diary days outside of the impact duration of prohibited hormonal therapies and medication potentially confounding efficacy will be included in baseline derivation. Details regarding the prohibited medications together with the impact duration are described in Section 6.3.

The mean daily value and change from baseline in mean daily value for each parameter will be analyzed using descriptive statistics by study treatment and week. The change from baseline over time by study treatment will be shown using line plots for means and 95% CI.

In addition, the mean daily value from the PSG nights will be summarized descriptively by study treatment and week. The mean value will be calculated using the same rule to calculate the primary endpoint (Section 4.2.1), i.e., if there are sleep diary data for both PSG nights, the mean value of the 2 nights will be used; if only 1 night is available, data from that one night will be used.

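### The Sleep Diary screening rules in SAP 4.4.2 use ≥, so a night of exactly zero reported sleep is deleted and sTST and sSE levels are biased upward

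*SAP*

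**What the plan says.** SAP Section 4.4.2 introduces a data-cleaning step: "SD assessments that do not logically make sense will be excluded from the analysis but will still be included in the listings". Any single criterion is enough: "Assessments that satisfy one or more of the below criteria will be excluded".

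The first three of its seven criteria compare durations:
- Criterion 1 removes an entry when time to fall asleep is at least as long as the bed-to-wake interval.
- Criterion 2 is "If total duration of awakenings ≥ duration between time going to bed and time waking up".
- Criterion 3 removes an entry when total awake time is at least the bed-to-wake interval less time to fall asleep. The minus sign is missing from the available text. It is read here as lost in conversion, since the sentence has no meaning without it.

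Table 4-6 of the same section defines sTST as the bed-to-wake interval "minus the time taken to fall asleep (Item 2) and total duration of awakenings (Item 4"). It takes sWASO from Item 4 alone, sLPS from Item 2 alone, and sSE as sTST over time in bed.

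Weekly means divide by the days with available data, and at least 4 of 7 days are required. Baseline is built in the same way from the 14 days before treatment, with at least 7 days. For the PSG nights, one night is used alone if the other is unavailable. SAP Section 4.4 adds: "For all exploratory endpoints, the ICEs will be handled according to the treatment policy. No missing data imputation is planned for these endpoints".

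The SAP Version History records that these exclusion rules were added in version 2.0 after blinded data review.

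**The concern.** An entry implying negative sleep time is arithmetically impossible and should go. An entry implying exactly zero sleep is an extreme value, but a possible one. A woman who never fell asleep could enter a time to fall asleep equal to her whole bed-to-wake interval, with no awakenings. SAP Section 4.1.1.3 says the diary forces an answer to each item, so she cannot skip the question, and neither document describes a separate response for a night without sleep.

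The ≥ sign treats her entry as illogical. Whether the night counts then depends on the outcome being measured, and the nights lost are the worst ones for sTST and sSE. The whole assessment is lost, so sWASO, sLPS and sNAW go with it. At stake is an accurate description of subject-reported sleep in a population enrolled for sleep disturbance.

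**Working it through.** The plan states no figure on this point, so there is none to reproduce. Notation: D = interval from going to bed to waking up, L = time to fall asleep (sLPS), W = total duration of awakenings (sWASO), all non-negative. The diary values below are assumptions, because the documents give none.

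**Step 1: what the criteria remove.** Table 4-6 gives sTST = D − L − W.
- Criterion 3: W ≥ D − L is the same as sTST ≤ 0.
- Criterion 1: L ≥ D implies D − L ≤ 0 ≤ W, so criterion 3 is also met. Here sTST = 0 only if L = D and W = 0.
- Criterion 2: W ≥ D implies W ≥ D − L, so criterion 3 is also met. Here sTST = 0 only if W = D and L = 0.

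A 15-minute grid (D 60–960 min, L and W 0–1020 min) confirms that criteria 1–3 exclude an entry if and only if sTST ≤ 0. Of 2135 grid entries with sTST = 0, 2013 meet criterion 3 alone, 61 meet criteria 1 and 3, and 61 meet criteria 2 and 3. These are grid counts, not expected frequencies.

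**Step 2: levels of sTST.** Take seven entries, k of them zero-sleep nights and the others averaging m. The mean is m(7 − k)/7 if the zeros are kept and m if they are deleted, a ratio of 7/(7 − k).
- m = 6 h, k = 1: 36/7 = 5.14 h kept, 6.00 h deleted, a rise of 0.86 h (51 min, 17%).
- k = 4: three nights remain and the week becomes missing.
- PSG-night summary, one night x and one night zero: x/2 kept, x deleted, so the value doubles.

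sSE moves by the same factor when time in bed is constant.

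**Step 3: sWASO and sLPS.** Assume D = time in bed = 480 min and six ordinary nights with L = 30 and W = 60, so sTST = 390 min (6.50 h) and sSE = 81.2%. Add one zero-sleep night. With deletion, sTST stays 6.50 h, sSE 81.2%, sWASO 60.0 min and sLPS 30.0 min. If the night is kept, sTST is 5.57 h and sSE 69.6%, and the other two depend on how it was entered:

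| Zero-sleep night entered as | sWASO if kept | sLPS if kept |
|---|---|---|
| L = 480, W = 0 | 360/7 = 51.4 min | 660/7 = 94.3 min |
| L = 440, W = 40 | 400/7 = 57.1 min | 620/7 = 88.6 min |
| L = 60, W = 420 | 780/7 = 111.4 min | 240/7 = 34.3 min |
| L = 0, W = 480 | 840/7 = 120.0 min | 180/7 = 25.7 min |

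Deletion makes sWASO look worse in the first two rows and better in the last two. It makes sLPS look better in the first three rows.

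**Step 4: an individual's change from baseline in sTST.** Assume 6.0 h at baseline and 6.5 h post-baseline on non-zero nights. With deletion the change is always +0.50 h.

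| Zero nights at baseline (of 14) | Zero nights post (of 7) | Change if kept | Bias from deletion |
|---|---|---|---|
| 0 | 1 | 5.57 − 6.00 = −0.43 h | +0.93 h |
| 2 | 1 | 5.57 − 5.14 = +0.43 h | +0.07 h |
| 2 | 0 | 6.50 − 5.14 = +1.36 h | −0.86 h |

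**Step 5: between arms.** Deletion raises an arm's mean sTST by m × p, where p is its share of zero-sleep nights. Randomization balances the baseline part in expectation. With a common m of 6 h (360 min), the post-baseline difference shrinks by (p placebo − p elinzanetant) × 360 min. Assumed rates give:
- 0.5% vs 0.25%: 0.9 min
- 1% vs 0.5%: 1.8 min
- 2% vs 1%: 3.6 min
- 3% vs 1%: 7.2 min

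**The case against.** The strongest objection is that an equality entry may itself be an error. If a woman reports two hours to fall asleep and then awakenings that fill every remaining minute, she has reported falling asleep yet sleeping for no time. Items on awakenings and on waking in the morning presuppose some sleep, and the diary screens are not in the documents. Keeping such an error moves a weekly mean as far as deleting a true zero does. This stands for entries with a reported sleep onset, and it is why a sensitivity summary is needed. It does not reach the entry L = D, W = 0, which reports no sleep and contradicts nothing in the definitions.

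It is also fair that the rules were set blind, that excluded entries stay in the listings, and that nights with any sleep above zero are kept. Only exact equality is affected, and it may be rare.

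A reader might infer that the deletion breaches the treatment-policy approach in SAP Section 4.4. It does not. That statement concerns intercurrent events (interruption, discontinuation, prohibited medication), whereas these criteria are data validation. A reader might also take criterion 2 as the operative rule. It reaches zero sleep only when time to fall asleep is zero; criterion 3 does the work.

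**Conclusion.** The point holds for sTST and sSE. The ≥ signs delete nights of exactly zero reported sleep because of their outcome value, and the weekly and PSG-night levels of both measures are biased upward whenever a genuine one occurs. If treatment reduces sleepless nights, the between-arm differences in sTST and sSE shrink in expectation. That direction assumes similar sleep on the remaining nights in both arms, and chance baseline imbalance is possible with about 39 women per arm.

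Three stronger readings are not supported:
- That sWASO generally looks too good. It does so only when the sleepless time was entered as awakenings; entered as time to fall asleep, sWASO looks worse and sLPS looks better.
- That each woman's improvement is overstated. The endpoint is change from baseline and the baseline loses such nights too, so the error can have either sign.
- That the bias is known to be material. The documents give no frequency of such entries and no assumed sTST effect, so the 0.9 to 7.2 min range only illustrates assumed rates.

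The affected endpoints are exploratory and summarized descriptively. The PSG primary endpoint and the PROMIS and ISI secondary endpoints are untouched. This is a desirable correction rather than an essential one.

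**What to change.** In SAP Section 4.4.2, change ≥ to > in criteria 1, 2 and 3. Together they then exclude exactly the entries with negative sleep time. Keep equality nights with sTST = 0 and sSE = 0%. Repeat the diary summary without the equality nights as a sensitivity check, since some may be entry errors. Add a table of excluded entries by criterion and treatment; the counts will overlap, because criterion 3 contains the other two.

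The cost is three operators in the SAP and program, one repeated summary and one count table. The number of equality entries can be counted on blinded data, which would show at once whether the choice matters. The downside is that an occasional erroneous entry landing exactly on zero sleep is kept in the main summary. Criteria 4 to 7 are unchanged.

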4.4.3 Hot Flash Daily Diary (HFDD)

- Frequency of HFs as measured by HFDD over time
- Change from baseline in proportion of days with participants rating "quite a bit" or "very much" sleep disturbance due to HF as measured by HFDD over time

Participants' assessments of HFs will be recorded electronically twice daily using the sponsor developed HFDD. The HFDD is completed in the morning after waking up (morning diary) and each evening at bedtime (evening diary) on the hand-held device. The HFDD assess the number of mild, moderate, and severe HFs experienced during the day (evening diary) and during the night (morning diary). Therefore, a diary day consists of the evening entry and the morning entry of the subsequent day.

Version 2.0 Page: 31 of 57

Mild HFs are defined as a "sensation of heat without sweating", moderate HFs are defined as a "sensation of heat with sweating, but able to continue activity", and severe HFs are defined as a "sensation of heat with sweating, causing cessation (stopping) of activity".

The following daily HF assessments will be aggregated to a mean daily frequency for each study week:

- moderate to severe nighttime HFs (morning diary)
- mild, moderate, and severe nighttime HFs (morning diary)
- moderate to severe HFs (morning and evening diary)
- mild, moderate, and severe HFs (morning and evening diary)

The mean daily frequency of moderate to severe nighttime HFs for a study week will be calculated as

total number of nighttime moderate to severe HFs during that week total number of available days with morning data during that week

The calculation of mild, moderate, and severe nighttime HFs, moderate to severe HFs and mild, moderate, and severe HFs will be calculated similarly to the above.

Study week will be assigned using the definition in Section 4.1.2. using the diary day as the date of observation. Data entered on the morning after the start date of treatment / randomization date will not be used in the calculation of baseline value but will be considered post-baseline for nighttime HFs. For the mean daily frequency using both the morning and evening diary (i.e., moderate to severe HFs and mild, moderate, and severe HFs), diary day 2 - 8 will be used for week 0.

A minimum of 4 days should be available within a study week for the derivation of mean daily frequency, otherwise it will be set to missing for that week. The baseline value will be calculated similarly using all available days with data during the 14 days prior to starting treatment. A minimum of 7 days should be available for the derivation of the baseline value. Only diary days outside of the impact duration of prohibited hormonal therapies and medication potentially confounding efficacy will be included in baseline derivation. Details regarding the prohibited medications together with the impact duration are described in Section 6.3.

A day would be considered as available if morning entry (of the subsequent day) is available when only morning diary is used, or if either evening entry or morning entry (of the subsequent day) is available when both evening and morning diaries are used.

The relationship between the frequency of HFs and WASO as measured by PSG will be explored. The PSG value as defined in Section 4.2.1 will be used in the analysis. Scatterplots showing the below will be produced separately for the actual values, change from baseline and percent change from baseline:

- mean daily frequency of moderate to severe nighttime HFs against WASO as measured by PSG
- mean daily frequency of mild, moderate and severe nighttime HFs against WASO as measured by PSG

Version 2.0 Page: 32 of 57

- mean daily frequency of moderate to severe HFs against WASO as measured by PSG
- mean daily frequency of mild, moderate and severe HFs against WASO as measured by PSG

The mean daily HFs for the same week the week 4 and week 12/EoT PSG assessments fall in will be plotted against each other. Scatterplots will be produced combining all visits on the same plot. In addition, the number of observations and Spearman's rank correlation coefficient and Pearson correlation coefficient with corresponding 95% CI will be computed and presented on the scatterplot.

The mean daily frequency of moderate to severe HFs (morning and evening diary) and mean daily frequency of mild, moderate, and severe HFs (morning and evening diary) as well as the change from baseline values will be analyzed using descriptive statistics by study treatment and week. The change from baseline over time by study treatment will be shown using line plots for means and 95% CI.

Sleep disturbances due to HFs are also assessed every morning as part of the HFDD. Participants provide a rating on their severity of sleep disturbances due to HFs in the previous night as

- 'not at all'
- 'a little bit'
- 'somewhat'
- 'quite a bit'
- 'very much'

To calculate the proportion of days with "quite a bit" or "very much" sleep disturbance due to HFs, the number of days with participants having reported "quite a bit" or "very much" sleep disturbance will be used.

The proportion of days with quite a bit or worse sleep disturbances due to HFs for each study week will be calculated using available data during that particular week as

number of days with rating 'quite a bit' or 'very much' sleep disturbance due to HFs during the week

total number of available days with morning data during that week

Study week assignment and number of available days for calculation of baseline and weekly values will follow the same rules as above for mean frequency of moderate to severe nighttime HFs.

The proportion of days with participants having reported "quite a bit" or "very much" sleep disturbance due to HFs as well as the change from baseline will be summarized using descriptive statistics by study treatment and week. The change from baseline over time will be shown using line plots for means and 95% CI by treatment group.

The proportion of days with participants having reported "not at all" or "a little bit" sleep disturbance due to HFs as well as the change from baseline will also be summarized using descriptive statistics by study treatment and week. The change from baseline over time will be

Version 2.0 Page: 33 of 57

shown using line plots for means and 95% CI by treatment group. The proportion of days with "not at all" or "a little bit" sleep disturbance due to HFs will be calculated similarly as proportion of days with "quite a bit" or "very much" sleep disturbance.

